#### 5.2.2 Other Factors

Potential Difficulties/Alternative Approaches: ((1) Each respondent will be compensated with \$20 worth of shopping vouchers as fair reimbursement for incidental expenses incurred for participating. The reimbursement can indirectly address potential recruitment issues by helping assuage any logistic issues the potential participants may have. (2) While we aim to recruit elderly who can read Mandarin, we may be limited by the language competency of the project staff. Nevertheless, we will try and arrange for conversant staff from other studies to supplement data collection. (3) The potential improvements to PMLs to be drawn from the expected findings may not directly address the needs of the elderly who are completely illiterate or have severe visual/cognitive impairment. Nonetheless, the pilot trials and subsequent RCT will benefit a large proportion of Singaporean elderly.

Withdrawals: Participants are free to withdraw their consent and discontinue their participation at any time without prejudice to him/her or effect on his/her medical care. However, the data that have been collected until the time of participant's withdrawal will be kept and analysed, to enable a complete and comprehensive evaluation of the study.

The study team may stop a participant's participation in the study at any time for one or more of the following reasons:

- Failure to follow the instructions of the Principal Investigator and/or study staff.
- The Principal Investigator decides that continuing the participant's participation could be harmful.
- The study is cancelled.

When a participant's participation in the study is withdrawn or stopped, their medications will be switched out from the Rx CapTM bottle to the usual twist-cap amber bottles or ziplock bags that is provided by SGH Pharmacy. For those randomized to receive bilingual PMLs, their bilingual

PMLs will be switched out to the usual English PMLs that are provided by SGH Pharmacy.

# 6. SAFETY MEASUREMENTS

#### 6.1. Definitions

Serious adverse event (SAE) in relation to human biomedical research, means any untoward medical occurrence as a result of any human biomedical research which:

- results in or contributes to death
- is life-threatening
- requires in-patient hospitalisation or prolongation of existing hospitalisation
- results in or contributes to persistent or significant disability/incapacity or
- results in or contributes to a congenital anomaly/birth defect
- results in such other events as may be prescribed

Adverse event (AE) in relation to human biomedical research means any untoward medical occurrence as a result of any human biomedical research which is NOT serious. Adverse event can be any unfavourable and unintended sign (including an abnormal laboratory finding), symptom, or disease possibly/ probably/ definitely associated with the participant in the human biomedical research.

#### 6.2. Collecting, Recording and Reporting of Serious Adverse Events (SAEs) to CIRB

Only related SAEs (definitely/ probably/ possibly) will be reported to CIRB. Related means there is a reasonable possibility that the event may have been caused by participation in the research. Please refer to the CIRB website for more information on Reporting Requirement and Timeline for Serious Adverse Events.

The investigator is responsible for informing CIRB after first knowledge that the case qualifies for reporting. Follow-up information will be actively sought and submitted as it becomes available.

Related AEs will not be reported to CIRB. However, the investigator is responsible to keep record of such AEs cases at the Study Site File.

#### 6.3. Safety Monitoring Plan

The PI, Co-Is, and study team will monitor and report any serious adverse events to the CIRB. As the study is expected to pose less than minimal risk to participants, the research team, overseen by the Principal Investigator, will perform data and safety monitoring. Research staff will ask participants about potential serious adverse events and more commonly known adverse events of their newly prescribed oral medication during their follow-up home visits.

#### 6.4. Complaint Handling

Any complaints will be directed to the research team for investigation, and overseen by the Principal Investigator.

We will adhere to prevailing COVID-19 control measures as recommended by the SGH Research Office

# 7. DATA ANALYSIS

### 7.1. Data Quality Assurance

All data collected on hardcopy survey forms will be transcribed into electronic data using double data entry by two different individuals and verified for consistency. Any discrepancies will be resolved by referring to source documents. Only study team members will handle and access these data.

# 7.2. Data Entry and Storage

All data with personal identifiers will be encrypted with password-protection. All physical research data including consent forms, data entry forms will be stored in locked cabinets at SGH. All soft copy research data will be coded, with participants' identifiers stored separately from research data, and only available on computers within the institution. Only de-identified data will be shared with study team members for data analysis and only the investigators and authorized personnel (principal investigator, co-investigators and research assistant) directly involved with the study will have access to the data. After study completion, research data will be stored on institution computers and remain password-protected, for a minimum of 7 years after completion of research study or date of publication of the research using the research data, whichever is later.

The Rx CapTM bottle measures patients medication adherence (Adherence is considered "met" when the new oral medication is taken based on both prescribed number of times per day and prescribed time of the day), each participant will be given 1-2 Rx CapTM pill tracker bottles. The electronic cap of the pill tracker records the date and time when the patient opens the vial to take his/her medication. This bottle does not collect any personal identifiers. A Rx CapTM account would be created for each participant. However, these accounts will be created by the study team using non-identifiable user information (i.e., "dummy" email addresses/usernames). As such, no personal identifiers will be stored in third-party databases.

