#### 2. HYPOTHESIS AND OBJECTIVES

Since the proposed study will collect preliminary data for informing the larger RCT, it does not aim to detect a significant difference in the trial outcomes in either pilot trial. Rather, its specific aims are:

AIM 1. To assess the feasibility of administering the intervention in the 2 "pilot" RCT versions. The proposed formative study will inform which of the 2 pilot trials will be scaled up and tested in the larger RCT. It will also result in finalization of the intervention and measurement material. AIM 2. To refine protocols for study participant recruitment, engagement and retention. AIM 3. To gain experience with and refine measurement of the medication-related outcomes.

A key outcome, medication adherence, will be measured using several approaches – self-report (ARMS; MedTake Assessment), which is easier and cheaper, and objective (pill count; electronic medication packaging [EMP]), which is tedious and expensive – during the 2 pilot trials. Comparison of the various approaches against the EMP (the most objective approach) will inform the choice of the measurement approach to be used for medication adherence in the larger RCT.

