#### 5.2.1 Measurements

Medication adherence: It will be measured in 4 different ways:

- 1. Adherence to Refills and Medications Scale (ARMS): A validated self-reported medication-adherence scale intended for patients with chronic diseases. The 12-item questionnaire consists of 2 sub scales adherence to refilling prescriptions and adherence with taking medications. Each item is structured using the Likert scale, with the following response options and corresponding scores: "none" (score of 1), "some" (score of 2), "most" (score of 3), or "all of the time" (score of 4). The range of possible total scores is 12 to 48. Lower scores indicate better adherence.
- 2. MedTake Assessment: A self-reported measure, recommended by Ministry of Health, Singapore for pharmacy staff when they provide pharmaceutical care services, that assesses patient adherence and knowledge to dose, dosage, indication, food or water coingestion, and regimen. A composite score (0–100%; higher ~ better) summarizes patient's ability to take medication safely.
- Pill count: A pill count, in context of the new oral medication, will be done.
  % adherence= ((quantity dispensed)-(quantity remaining))/((prescribed number of pills per day)×(no.of days between dispensing date and interview))

Electronic medication packaging [EMP]: All participants will be dispensed their new oral

medication in a Rx CapTM medication bottle (www.rxcap.com), whose Rx CapTM Bluetooth smart cap will automatically track medication usage every time it is opened. Project staff will sync participants' data, collected and stored within the Smart Cap, at each home visit, and import it to the Rx CapTM Engage platform for analysis. Continuous (% adherence to prescribed regimen; 0-100%) and categorical variables (not at all; partially; fully) for medication adherence will be derived. Rx CapTM medication bottle is not being used in standard clinical practice yet and it is used for this proposed research only. To our best knowledge, Rx CapTM medication bottle is not validated for use clinically yet.

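### The EMP score requires correct timing and pill count cannot see timing, so their planned agreement analysis mixes measurement disagreement with a difference in definition

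*Protocol*

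**What the plan says.** EMP adherence is described in two places. Section 5.2.1 (Measurements) says "Continuous (% adherence to prescribed regimen; 0-100%) and categorical variables (not at all; partially; fully) for medication adherence will be derived", with no mention of timing. Section 7.2 (Data Entry and Storage) adds the operative rule, cut here one word short: "Adherence is considered 'met' when the new oral medication is taken based on both prescribed number of times per day and prescribed time of the" [...]. The same section says that the cap "records the date and time when the patient opens the vial to take his/her medication". Neither section gives a time window or says whether the score is built per dose or per day.

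Pill count is defined in Section 5.2.1 as "adherence= ((quantity dispensed)-(quantity remaining))/((prescribed number of pills per day)×(no.of days between dispensing date and interview". Its inputs are tablets gone, tablets prescribed per day and days elapsed.

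Section 8.2 plans Bland-Altman plots (continuous) and Cohen's kappa (categorical) between EMP and each of the three other adherence measures. Section 2 states the purpose: "Comparison of the various approaches against the EMP (the most objective approach) will inform the choice of the measurement approach" for the larger RCT.

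**The concern.** Bland-Altman limits and kappa describe measurement agreement only when both methods aim at the same quantity. Here they do not. A participant who takes every tablet, some of them at the wrong time of day, is 100% adherent by pill count and less than 100% by EMP, with no error in either device. The timing condition can only lower the EMP score relative to a count of the same openings, so the distortion runs one way.

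The choice of adherence measure for the larger RCT is at stake. From the planned analysis alone, a low kappa or a large bias could mean that pill count is bad at counting doses, or only that it does not record timing. The first is a reason to distrust pill count. The second is a known property of the method and needs no pilot data to establish.

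**Working it through.** The protocol states no expected agreement, off-time rate, time window or device error, so there is no figure to reproduce. All rates below are assumptions.

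**Step 1. Participants who take every dose.** Let p be the probability that a dose is on time (independent doses) and k the number of doses per day. Pill count is 100%.

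- Scored per dose, expected EMP is p, so the gap is 100 × (1 − p), whatever k is.
- Scored per day (all doses that day must be right), expected EMP is p^k, so the gap is 100 × (1 − p^k).

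| On-time p | Per dose, any k | Per day, k = 1 | Per day, k = 2 | Per day, k = 3 |
|---|---|---|---|---|
| 1.0 | 0 | 0 | 0 | 0 |
| 0.9 | 10 | 10 | 1 − 0.81: 19 | 1 − 0.729: 27 |
| 0.8 | 20 | 20 | 1 − 0.64: 36 | 1 − 0.512: 49 |

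**Step 2. The top EMP category.** Suppose full adherence means 100% over 14 days (assumed; the protocol gives no cut-point). At p = 0.9, a participant who takes every dose reaches it with probability 0.9^14 = 23% once daily and 0.9^28 = 5% twice daily. This holds under either scoring unit. Pill count puts the same participant in the top category every time.

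**Step 3. A mixed population.** This is a simulation of 200,000 patients over 14 days with error-free devices. Assumptions: 30% take every dose; the rest take each dose with a patient-specific probability from Beta(6,2), mean 0.75; the off-time share varies by patient (Beta, concentration 5); categories are none, partial and 100%. EMP is scored per dose. Results are pill count minus EMP, once daily:

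| Off-time share | Bias (points) | Limits of agreement | Kappa |
|---|---|---|---|
| 0% | 0 | 0 to 0 | 1.00 |
| 5% | 4.1 | −13.5 to 21.8 | 0.74 |
| 10% | 8.2 | −16.1 to 32.6 | 0.54 |
| 20% | 16.5 | −16.6 to 49.5 | 0.26 |

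As a check, mean dose-taking is 0.3 × 1 + 0.7 × 0.75 = 0.825, and 0.825 × 0.20 = 16.5 points. Twice daily, bias is similar and kappa is lower: 0.68, 0.44 and 0.16 at 5%, 10% and 20% off-time. The negative lower limits come from applying symmetric limits to skewed differences; no simulated difference is negative.

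The scoring unit matters separately. Per-day scoring with twice-daily dosing gives a bias of 11.7 points with no off-time doses at all, because missing one of two doses loses the whole day: 0.7 × (0.75 − 42/72) = 0.117. At 10% off-time the bias is 24.1 points.

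**Step 4. How much of the disagreement is definitional?** Random pill-count error was added to the once-daily model, and the share of the mean squared difference due to definition was computed:

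| Pill-count error SD | 5% off-time | 10% | 20% |
|---|---|---|---|
| 5 points | 80% | 90% | 96% |
| 10 points | 50% | 69% | 85% |
| 20 points | 20% | 36% | 58% |

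With no off-time doses the share is 0%.

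**Step 5. Effect of removing the timing condition.** Scoring the same simulated openings by count alone, per dose, gives zero bias and kappa 1.00. In the error-free per-dose model, all the disagreement comes from the timing rule.

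**The case against.** The strongest reply is that timing belongs in adherence. The intervention is a label that carries instructions, EMP is the declared reference, and if the target is adherence to the whole regimen, then blindness to timing is a real limitation of pill count that a method comparison should reveal. This stands as a defence of the timing score, and that score should be kept. It does not defend having it as the only EMP score in the pill-count comparison, because the result then cannot separate miscounted doses from unrecorded timing.

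It can also be said that this is a descriptive pilot of 40 patients, that the results only inform a choice, and that derivation detail may sit in a statistical analysis plan not shown here. That limits the consequence. But the timing rule, the pill-count formula, the comparison and its use are all fixed in the protocol itself, and its two descriptions of EMP adherence differ.

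Three stronger readings are tempting and are not supported:

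- A reader might infer that the agreement analysis will mostly reflect definition. The share in Step 4 runs from 0% to over 90%, and the protocol gives nothing to locate it. If the time of day is judged coarsely, such as morning or evening, few doses may be off-time.
- A reader might infer that the bias grows with dosing frequency. In Step 1 that is true only of per-day scoring, which the protocol does not state.
- A reader might infer that a valid measure will be discarded. No agreement threshold or rejection rule exists, so this is a risk only.

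**Conclusion.** The concern holds in a limited form. EMP as defined in Section 7.2 and pill count as defined in Section 5.2.1 measure different quantities, and the comparison in Section 8.2 treats the difference as disagreement, in a direction that lowers EMP. The size cannot be fixed from the protocol. For participants who take every dose with 10-20% off-time (assumed), the gap is 10-20 points per dose; per day it rises to at most 36 points twice daily and 49 three times daily. In the assumed mixed population, an error-free pill count would show kappa of 0.54 once daily or 0.44 twice daily at 10% off-time. This should be corrected before the agreement results are used to choose a measure. It does not invalidate the pilot, because the raw time stamps allow either score to be derived.

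**What to change.** In Section 5.2.1, define two EMP scores from the cap time stamps:

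- (a) A count-only score: dosing openings divided by doses prescribed, over the same dispensing-to-interview window as pill count. Section 5.2.1 bounds EMP at 0-100% while the pill-count formula has no upper bound, so apply one rule for values above 100% to both measures. Use this score for the Bland-Altman and kappa comparison with pill count.
- (b) The existing number-plus-timing score, kept as a separate outcome and as a secondary comparison with pill count. State its time window and whether it is scored per dose or per day.

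Reconcile the EMP descriptions in Sections 5.2.1 and 7.2, and name in Section 8.2 which score enters which analysis.

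The cost is protocol wording and one more adherence score to derive and report. It needs no new data and adds no burden for participants.

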# 8. SAMPLE SIZE AND STATISTICAL METHODS

#### 8.1. Determination of Sample Size

Sample size/ power calculation is an important component for a RCT. However, as the proposed study is to conduct two pilot versions of a RCT, aiming to obtain preliminary data that will inform the sample size/ power calculation of a following, larger RCT, no sample size estimation has been done for the proposed study.

# 8.2. Statistical and Analytical Plans

As we are conducting 2 "pilot" versions of a RCT, most analyses will be descriptive and exploratory. In both pilots, trial outcomes will be summarized using measures of central tendency and dispersion (e.g., mean and standard deviation). In Pilot Trial A, significant difference in change, from baseline to 2 weeks post-randomization, in the 3 medication-related outcomes between the 2 arms will be assessed using t-test (for continuous variables, e.g. difference in change in ARMS

scores or MUSE scores) or chi-square test (for categorical variables, e.g. difference in change in % with complete PML understanding or % with complete adherence as per EMP). In Pilot Trial B, significant difference, at 2 weeks post-randomization, in the 3 medication-related outcomes between the 2 arms will be assessed using t-test (for continuous variables, e.g. difference in the ARMS scores or MUSE scores) or chi-square test (for categorical variables, e.g. difference in % with complete PML understanding or % with complete adherence as per EMP). For agreement between medication adherence assessed using EMP and that assessed using the 3 other approaches, Bland-Altman plots (adherence considered as continuous) and Cohen's kappa43.45 ( $\varkappa$ ; adherence considered as categorical) will be used. While our findings will only provide a general sense of the intervention impact, they will primarily inform which measures to use for the subsequent RCT and for determining its optimal sample size. We will also tabulate participation rates and loss to follow-up.

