Need for rigorous PML intervention studies: A recent review on the impact of improved PMLs concluded that intervention studies that test PML improvements in a rigorous manner are lacking. It also recommended that future studies should extend research to outcomes more proximal to medication taking – medication adherence and medication management self-efficacy. In Singapore, the only published PML intervention did show bilingual PMLs (vs English PMLs) to increase PML understanding. However, it, again, did not assess medication adherence and medication management self-efficacy. Thus, rigorous intervention studies that assess the impact of improved PMLs on a range of medication-related outcomes are needed.

Our proposal is the *first step* towards a well-informed, rigorous intervention study or RCT that will provide concrete evidence on the impact of the provision of bilingual PMLs on key medication-related outcomes – medication adherence, medication management self-efficacy, and PML understanding. The experience gained, and data collected, through the conduct of the 2 pilot trials, funded through the current proposal, will allow us to choose the optimal trial design, and refine protocols for recruitment, engagement and retention of study participants for the larger RCT as well as determine variability in outcomes so that the larger RCT is appropriately powered to detect meaningful differences in the outcomes – an immediate output of our proposed project will be a grant proposal to a national level grant mechanism for the conduct of the larger RCT. Eventually, the 2 pilot trials, and the subsequent larger RCT, will contribute to implementing patient-centered PMLs.

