#### 5.1 Study Design

Briefly, in Pilot Trial A, all will be first given the usual English PML for their new medication. There may be non-standardized, ad-hoc noting on the PML by the pharmacy staff when participant is deemed not able to understand the English PML. All content of the non-standardized, ad-hoc noting including pictures drawn will be recorded. Then, *at 2 weeks post-recruitment*, their baseline level of the 3 medication-related outcomes (w.r.t. the new medication) will be gauged, after which they will be *randomized* (1:1; block randomization, block of 4) to one of 2 PMLs (Bilingual [intervention] or English [usual care]) at their home. Follow-up assessment of the 3 medication-related outcomes will be also be done at 2 weeks post-randomization at their home.

In Pilot Trial B, participants will be *randomized* (1:1; block randomization, block of 4) *just after recruitment* to one of 2 PMLs (Bilingual [intervention] or English [usual care]) in the DMC pharmacy. There may be non-standardized,ad-hoc noting on the PML by the pharmacy staff when participant is deemed not able to understand the English PML. All content of the non-standardized, ad-hoc noting pictures drawn will be recorded. The 3 medication-related outcomes will be assessed at 2 weeks post-randomization at their home.

All participants will receive their usual medical care, and usual medication counselling at the DMC pharmacy for all their medications. All medications, other than the new oral medication (which made them eligible, and whose PML will be intervened upon), will be dispensed with usual English PMLs.

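### Pilot Trial A: the t-test on change is valid but usually less precise than follow-up adjusted for baseline, and a plain chi-square does not fit the stated difference in change in percentages

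*Protocol*

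**What the plan says.** Protocol section 5.1 has Pilot Trial A participants use the English label for two weeks, after which "their baseline level of the 3 medication-related outcomes (w.r.t. the new medication) will be gauged". Section 5.2 adds that the arm is disclosed only after that assessment. Outcomes are measured again two weeks after randomisation.

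Section 8.2 fixes the between-arm comparison in Pilot Trial A. For continuous outcomes, "significant difference in change, from baseline to 2 weeks post-randomization, in the 3 medication-related outcomes between the 2 arms will be assessed using t-test". For categorical outcomes it names a "chi-square test (for categorical variables, e.g. difference in change in % with complete PML understanding or % with complete adherence as per EMP". Pilot Trial B has no outcome baseline and gets a cross-sectional "chi-square test (for categorical variables, e.g. difference in % with complete PML understanding or % with complete adherence as per EMP". In both pilots, "trial outcomes will be summarized using measures of central tendency and dispersion (e.g., mean and standard deviation".

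On purpose, section 2 says of the study that "it does not aim to detect a significant difference in the trial outcomes in either pilot trial". Section 1 says that the pilots should "determine variability in outcomes so that the larger RCT is appropriately powered to detect meaningful differences in the outcomes".

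**The concern.** There are two separate issues.

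**Continuous outcomes.** Subtracting the whole baseline value is the best use of it only when the regression slope of follow-up on baseline is near 1. When the slope is smaller, the subtraction adds noise. Pilot Trial A pays for an extra home assessment to obtain this baseline, so the question is how much of its value the analysis gives up.

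**Categorical outcomes.** The quantity named is a difference between arms in a paired net change. A Pearson chi-square compares independent distributions. The protocol uses the same words for Pilot Trial B, where they fit. In Pilot Trial A an analyst must choose a table, and the choice determines which hypothesis is tested.

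At stake are the precision of the exploratory estimates, the meaning of the categorical p-value, and whether the report shows what is needed to size a baseline-adjusted larger trial.

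**Working it through.** The protocol gives no power, alpha, SD or correlation, so there is no figure to reproduce.

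**Inputs**
- Arm size: 40 patients (section 5), 1:1 to Pilot A or B, then 1:1 to arm. 40 / 2 / 2 = 10 per arm before loss.
- Assumed: r as a range, SD standardised to 1, equal SDs at both visits unless stated, two-sided 5%.

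**Continuous outcomes.** Standard error of the arm difference at 10 per arm:
- Change: sqrt((2/10) × 2(1 − r)) = sqrt(0.4(1 − r)), 18 df, t = 2.101
- Follow-up alone: sqrt(0.2) = 0.447, 18 df; half-width 2.101 × 0.447 = 0.940
- Follow-up adjusted for baseline: sqrt(0.2(1 − r²) × 17/16), 17 df, t = 2.110. The factor 17/16 is the small-sample cost of estimating the slope with 20 patients.

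| r | Half-width, change | Half-width, adjusted | Adjusted v change |
|---|---|---|---|
| 0.3 | 1.112 | 0.928 | 17% narrower |
| 0.5 | 0.940 | 0.842 | 10% narrower |
| 0.7 | 0.728 | 0.695 | 5% narrower |
| 0.9 | 0.420 | 0.424 | 1% wider |

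The two are equal at r = 0.882 by standard error and 0.867 by interval width. Below r = 0.5, 2(1 − r) exceeds 1, so change is less precise than follow-up alone. In simulation the t-test on change had a type I error of 0.049 to 0.052, so its validity is not in doubt.

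**Unequal SDs.** Let k be follow-up SD divided by baseline SD. The variance ratio, change over adjusted, is (k² + 1 − 2rk) / (k²(1 − r²)) × 16/17. Over r = 0.3 to 0.9:
- k = 0.75: about 1.67 to 2.05, a larger gain than with equal SDs
- k = 1.33: about 0.94 to 1.15. Change has the slightly smaller standard error for r of about 0.55 to 0.87.

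**Categorical outcomes.** Possible readings of the chi-square:
1. *Improved / same / worse by arm.* This tests whether the arms have the same mix of changes. Take 0/10/0 in one arm and 4/2/4 in the other: net change is zero in both. Expected counts are 2, 6 and 2 per arm, so chi-square = 4 × (2²/2) + 2 × (4²/6) = 8 + 5.33 = 13.3 on 2 df, p = 0.001. This is a constructed extreme. If 10% v 50% of patients change category with zero expected net change in both arms, the test rejects in 35% of simulated trials.
2. *Improved / not improved.* Patients who worsen are counted with those who stay the same, so net change is not tested.
3. *Baseline and follow-up percentages treated as independent.* This does target the named quantity, but it ignores the within-patient correlation phi. With equal prevalence at both visits the true variance is (1 − phi) times the one used, so the level is 2P(Z > 1.96/sqrt(1 − phi)). That is 1.9% at phi = 0.3 and 0.6% at phi = 0.5. Simulated at 10 per arm and 50% prevalence, it is 1.7–1.9% and 0.5–0.6% with pooled variance, and 3.8% and 1.4% unpooled.

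Under equal arms at these correlations, reading 1 rejected in 3.5% and 2.3% of simulated trials, and reading 2 in 2.6% and 1.4%. None exceeded 5%.

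**The case against.** **The t-test is valid, and adjustment could be left to an analysis plan.** Validity stands: a reader might infer bias or an inflated error rate, and neither is there. But section 8.2 does not leave the method open. It names an unadjusted test, so an improvement to that stated choice is a fair point.

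**The gain depends on unknown r and SDs.** This stands. A reader might take the loss as certain for any r below 0.87. That holds only with equal SDs. At k = 1.33 the advantage disappears or slightly reverses.

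**Some chi-square could test the change.** This stands in part. Reading 3 aims at the right quantity, and a Wald-type chi-square for paired data could test it properly. So the protocol does not support the claim that no chi-square can do so. The narrower point remains: the bare term does not select such a test, and the ordinary tables either miss the target or ignore the pairing.

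**Follow-up proportions already answer the question.** Since baseline precedes disclosure of the arm, the expected arm difference at follow-up equals the expected difference in change. This is correct, and it is why the fix uses that comparison.

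**Sizing of the larger trial is not harmed.** A reader might infer that the larger trial will be sized on the SD of change. Nothing in the protocol says so. The correlation can also be recovered from the two visit SDs (s1, s2) and the change SD (sd), as (s1² + s2² − sd²)/(2·s1·s2). What remains is that the listed summaries, means and SDs of the outcomes, do not by themselves show r or the residual SD.

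**Small counts might seem to call for an exact test, in Pilot B too.** The protocol does not need this change. At 10 v 10 the unconditional exact test has the same 5% rejection region as the uncorrected chi-square. After loss to 8 v 8 the chi-square's maximum level is 7.7%, but the exact test then has 26% power against Fisher's 25% for 30% v 70%. In a study not aimed at significance, this is a matter of preference.

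**Conclusion.** The point holds as a modest improvement to the stated analysis. It is not an error that invalidates results.

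- **Continuous outcomes:** with 10 per arm and equal SDs, adjusting for baseline narrows the interval by about 17%, 10% and 5% at r = 0.3, 0.5 and 0.7, and stops helping at about r = 0.87. The gain is larger if follow-up is less variable than baseline, and absent or slightly negative if follow-up SD is about 1.33 times baseline SD.
- **Categorical outcomes:** the test named is not matched to the quantity named. The consequence is a wrong hypothesis or lost sensitivity, not excess false positives.

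Importance is low to moderate, because the pilot is exploratory and disclaims significance as an aim. The algebra is certain. The size in this trial is not, because r and the SDs are assumed.

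**What to change.** In section 8.2, for Pilot Trial A:

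- **Continuous outcomes:** regress each outcome at two weeks post-randomisation on arm and its own baseline value. Report the adjusted difference with 95% CI, the residual SD and the baseline-to-follow-up correlation with its CI, for use in sizing the larger trial.
- **Categorical outcomes:** replace the test of change with a comparison of follow-up proportions by arm, as a risk difference with a score-based 95% CI (for example Newcombe). Show the baseline-by-follow-up table for each arm descriptively. Baseline information is still used, because section 5.2.1 also derives label understanding and EMP adherence as continuous percentages, which the regression adjusts.

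Pilot Trial B's chi-square and the choice of exact test need not change.

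**Cost:** wording only, no new data. One residual degree of freedom is lost (17 v 18). If r is near 0, the adjusted interval is up to about 4% wider than follow-up alone (0.973 v 0.940). The estimate of r will be rough: with 20 patients and an observed r of 0.5, its 95% CI is 0.07 to 0.77, so the larger trial should be sized over that range.
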